answer questions will be thanked for their time and the phone call will end. Women may ask to stop the screening phone call at any time. The pre-screen questionnaires will be administered to assess insomnia status. The full written ISI will be administered at Visit 3 and Visit 4. The ISI may be administered again over the phone before Visit 1 or Visit 2, if one of these visits has been delayed, and insomnia status must be reassessed. Preliminary screening determination will include questions modified from the Berlin Questionnaire to exclude women at high risk for obstructive sleep apnea. We will also ask some questions drawn from the PHQ-9 which will be completed at the first visit. The PHQ-2 asks specifically about frequency of anhedonia and depression in the past two weeks. We will exclude participants who do not qualify initially on the phone screen. Anyone identified as being at risk for depression will be instructed to assess their symptoms with their physician and be offered resources for where they can seek additional help. The full PHQ-9 will be administered at Visit 1, Visit 3, and Visit 4.

Following the screening phone call, women who are interested and preliminarily eligible to complete the screening process will be mailed or emailed the pre-screening materials, a copy of the informed consent and a cover letter describing the pre-screening procedures. The pre-screening materials include hot flash and sleep diaries to be completed at home for 1 week. BWH study staff will call potential participants to determine whether they received these materials and review how to complete them. Women who are currently taking medications to help them sleep will be asked if they are willing to refrain from taking sleep medications for the duration of the study (approx. 6 weeks) beginning with the tracking period. Women who agree to complete the pre-screening diaries will be contacted by phone after ample time has elapsed. During this call, the BWH study staff member will review the diary entries to determine eligibility for the screening visit. The pre-screening diaries are used to reduce subject burden by only scheduling subjects eligible for the screening visit.

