Treatment period: At the Randomization Visit, eligible women will be randomized to 4 weeks of suvorexant or placebo. Pre-treatment symptom measures will be assessed at the Randomization Visit and interim and final on-treatment symptom measures will be assessed at the Interim Treatment Visit and Final Treatment Visit, respectively. The primary endpoint measures will be obtained at the Final Treatment Visit, conducted after 4 weeks on treatment. Participants will complete sleep and hot flash diaries for the 4 weeks they are on treatment and will be sent an Actiwatch and Biolog monitor to wear for one week (Actiwatch) and for one 24-hr period (Biolog) before returning them at the Final Treatment Visit. Participants will also be asked to provide saliva samples for two consecutive days in between Visits 1 and 2 and Visits 3 and 4. These samples will be used to measure cortisol. We have implemented these procedures in prior clinical trials

with efficiency and high levels of adherence. Adverse events will be assessed at each study visit using spontaneous-reporting adverse event procedures employed in our other clinical trials.

Intervention design: Suvorexant and identical placebo will be obtained from Merck and stored in the Brigham and Women’s Hospital Research Pharmacy. The Research Pharmacist will generate a confidential randomization schema using a block size of 4 to balance the one-to-one treatment assignment between the two study arms. Study participants and all study personnel, including those entering data, will be blinded to the assignment. Only the Research Pharmacist will be unblinded to treatment assignment.

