At the Randomization Visit, a one-week supply of suvorexant 10-mg pills or identical placebo will be given to each participant. Participants will be instructed to start taking 10-mg nightly for the first 7 days. At the Interim Treatment Visit conducted after one-week on treatment, participants who do not have treatment-limiting side effects will be instructed to increase the dose to 20-mg nightly. After the Interim Treatment Visit, women unable to tolerate a 20-mg dose will be given the option to reduce to a 10-mg dose. Consistent with FDA-approved directions, suvorexant will be started at 10-mg to first establish tolerability and then expected treatment efficacy will be optimized by increasing to the target 20-mg dose 7 days later. Any unused medication will be returned at the Final Treatment Visit, and unused pills will be counted as an indicator of adherence. If participants are unable to attend the Final Treatment Visit in person, subjects will complete remaining study procedures remotely, and will mail back any unused medication for a measure of adherence. Participants will also return the Actiwatch, Biolog monitor, and saliva samples by mail if a remote Final Treatment Visit is performed. In addition to answering questionnaires remotely, a study clinician will call the participant for safety monitoring. Study staff will review responses to the PHQ9 before ending study visits, and a study clinician will query participants directly about suicidal ideation and other adverse events at study visits while participants are on medication. Participants will not be informed of their treatment assignment at the Final Treatment Visit to maintain the blinding for study personnel.

Protocol Schema

[figure not shown]

Table of Procedures

		Screening		Intervention		
		Pre-V1	V1	V2 Random-ization	V3	V4
Study Week		-1	0	1	2	5
Weeks on Medication				0	1	4
Visit Location		Phone + Mail	Office	Office	Office	Office
General/ Screening Assessment	Screening Consent	X				
	Written Informed Consent		X			
	Health and Personal History Questionnaire		X			
	Insomnia Diagnostic Assessment		X			
	Medical History		X			
	Concomitant Medications	X	X	X	X	X
	Screening Assays (hepatic, renal, HCG, tox)		X			
	Hormone Assays (FSH, estradiol, progesterone)		X			
	Berlin Questionnaire	X				
Neck circumference		X				
PHQ-2	X					
Vitals	Height/Weight/Heart rate/Blood Pressure		X	X	X	X
	Waist to Hip Ratio		X			
Medication Dispensing & Instructions				X	X	
AE Reporting			X	X	X	X

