Sleep Assessment	Sleep Diary ^b					→
	Actigraphy Watch ^c		→			→
	ISI	X		X	X	X
	PSQI			X		X
	DBAS			X		X
	Sleep Locus of Control Scale			X		X
Hot Flash Assessment	Hot Flash Diary ^b					→
	Hot Flash Monitor ^a HFRDIS		→	X		X
Hyperarousal	Salivary Cortisol		→			→
	Hyperarousal Scale			X		X
	PSAS			X		X
Exploratory Measures	PHQ-9		X		X	X
	CES-D			X	X	X
	ASI-3			X	X	X
	GAD-7			X	X	X
	MENQOL			X		X
	PGI (Severity & Improvement)		X		X	X

Study procedures completed between study visits: a = for 24 hours; b = daily for 6 weeks; c = daily for 1 week DSM-V¹ = Diagnostic and Statistical Manual of Mental Disorders, 5th Edition, HCG = Human Chorionic Gonadotropin, FSH = Follicle Stimulating Hormone, ISI = Insomnia Severity Index, PSQI = Pittsburgh Sleep Quality Index, PSAS = Pre-Sleep Arousal Scale, DBAS = Dysfunctional Beliefs and Attitudes about Sleep Scale, HFRDIS = Hot Flash Related Daily Interference Scale, PHQ-8 = Patient Health Questionnaire Depression Scale, CES-D, Center for Epidemiological Studies Depression Scale, ASI-3 = Anxiety Sensitivity Index, GAD-7= General Anxiety Disorder Questionnaire MENQOL = Menopause-Specific Quality of Life Questionnaire, PGI-Patient= Clinical Global Impression Scale – Patient

Study assessments and procedures include the following:

1. Insomnia and sleep quality symptoms will be measured using:
 1. DSM 5 diagnostic interview for chronic insomnia. A clinical diagnosis of chronic insomnia will be made using the DSM-V diagnostic interview, allowing for associated hot flashes (see Inclusion Criteria).
 2. Sleep diary. Consistent with research consensus guidelines of insomnia,²⁵ a standard daily sleep diary will be completed to quantify perceived total sleep time, sleep latency, wake time after sleep onset, number of awakenings, sleep efficiency, and sleep quality.
 3. The Actiwatch actigraphic watch (Philips Respironics, Murrysville, Pennsylvania) will be worn on the non-dominant wrist to quantify sleep patterns based on acceleration and movement and the data output will be analyzed using standard actigraphic analysis algorithms.
 4. The Insomnia Severity Index (ISI), a 7-item self-rated questionnaire (range 0–28) used to assess the severity of insomnia symptoms over the past 2 weeks.²⁶
 5. The Pittsburgh Sleep Quality Index (PSQI), a 19-item self-rated measure of global sleep quality (range 0–21) occurring during the past one-month.²⁷

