Biolog skin conductance hot flash monitor: This is a widely used and validated ambulatory skin conductance monitor (UFI, Morro Bay, CA) that will be worn to quantify the number of objectively measured hot flash events by detecting changes in skin conductance on the sternum. This approach measures physiologic hot flashes independent of recall for the events, thereby eliminating potential recall bias for nighttime events.

Surgical Interventions

No surgical interventions will be used in this study.

VI. BIostatistical Analysis

Overview of analytic plan: The primary hypothesis for this trial is that suvorexant is superior to placebo in treating insomnia symptoms. The primary endpoint is the change in the ISI score from

baseline to 4-week follow-up. Exploratory analyses will examine the effect of suvorexant relative to placebo on secondary endpoints of sleep continuity parameters and diary-reported hot flashes, and exploratory endpoints including mood, anxiety, hot flashes (skin-conductance monitor), physiological stress (salivary cortisol), and quality of life.

Study endpoints:

Primary endpoint:

1. The primary endpoint is the change in the ISI score from baseline to 4-week follow-up.

Secondary endpoints:

1. Diary-reported WASO, SOL, TST, and sleep efficiency
2. Number of hot flashes reported on the diary separately during the day and night

Exploratory endpoints:

1. Actigraphy-measured WASO, SOL, TST, and sleep efficiency
2. Depressive symptoms
3. Anxiety symptoms
4. Quality of life
5. Number of hot flashes measured on the skin-conductance monitor
6. Physiological Stress (measured by salivary cortisol)

Primary analysis: The primary analysis will compare the within-person change in outcomes at Week 4 relative to baseline using general linear models, adjusting for baseline values and relevant covariates showing group differences at baseline. Diagnostic methods will be used for all models to assess their distributional assumptions, model adequacy, and to examine potential outlying or influential data points. An additional exploratory ISI responder analysis will be conducted using logistic regression to determine whether there is a group difference in the proportion of women that had a 8-point reduction in the ISI score from baseline.⁴¹

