Missing data: Every effort will be made to avoid missing data and to include all randomized subjects in the analysis. The effects of missing information on statistical power have been addressed to the degree feasible in the sample size calculations. Missing data will be imputed as last observation carry forward.

Power and sample size: In total, up to 90 women will be enrolled in this study. Treatment will be randomly assigned in a 1:1 ratio. Allowing for 10% to be lost to follow up after consent (n=8) and 15% to be lost after randomization (n=12), we expect to randomize up to 72 participants to treatment and complete 60 subjects (30 per treatment group). This sample size provides enough subjects to have 80% power for the primary hypothesis, assuming that there is a between-group difference in the change from baseline to study-end in the ISI score of 4 points with a standard deviation of 4.86 (two-sided alpha = 0.05). Previous clinical trials have found between-group differences in ISI change scores of 5.2 points¹¹ when women with hot flash-related insomnia were randomized to CBTi vs. behavioral control and between-group differences in ISI change scores of 2–3 points⁴³ when women with hot flashes and sleep disturbance were randomized to the SSRI citalopram vs. placebo. The standard deviation in the change in ISI for these interventions and controls arms was selected because it is in the midpoint of standard deviations from previous studies, which ranged from 4 to 6.^{11,43} Data from the Phase 3 suvorexant trials were not used to support our sample size calculations because of differences in the sleep profile between our hot flash-related insomnia population (see Preliminary Data) and the general insomnia population

enrolled in suvorexant trials for which there was no minimum ISI score required for eligibility (mean ISI ~14).⁴⁴

VII. RISKS AND DISCOMFORTS

Potential risks of study procedures:

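### Last observation carried forward is the only missing-data rule for the primary ISI endpoint, and no planned analysis would reveal the bias it can cause if losses differ between arms

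*Combined protocol and SAP*

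**What the plan says.** The missing-data paragraph of Section VI aims to "include all randomized subjects in the analysis" and then gives a single rule: "Missing data will be imputed as last observation carry forward". Under Primary analysis, "The primary analysis will compare the within-person change in outcomes at Week 4 relative to baseline using general linear models", adjusted for baseline. The model diagnostics and the exploratory responder analysis named there do not address missing data.

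Section V fixes the endpoint in time: "The primary endpoint measures will be obtained at the Final Treatment Visit, conducted after 4 weeks on treatment". The Table of Procedures marks the ISI at pre-screening, V2 (randomisation), V3 (1 week on medication) and V4 (4 weeks). The Pre-Screening text in Section IV names fewer visits: "The full written ISI will be administered at Visit 3 and Visit 4". The two should be reconciled, because V2 supplies the baseline that would be carried forward. The ISI is "used to assess the severity of insomnia symptoms over the past 2 weeks" (Section V, assessments, item 1.4), and the planned dose increase takes place at V3 (Section V, Intervention design).

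Three places provide for remote completion: the Off-Study Criteria (Section III) for women who are dropped, Treatment Assignment and Randomization (Section IV) for women who choose to stop, and Intervention design (Section V) for those who cannot attend the final visit. Only the last is tied expressly to a visit. The Off-Study Criteria do not say when a dropped woman's final questionnaires are completed.

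**The concern.** For a woman with no Week-4 ISI, LOCF can draw on only two scheduled values. One is baseline, which makes her change exactly zero. The other is the V3 score, whose two-week recall is half pre-treatment and which reflects only the starting dose. The Week-4 model then treats that value as observed.

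Both arms are likely to improve to some degree, so carrying an early value forward pulls an arm's mean towards zero in proportion to its losses. If the arms lose different numbers, the pull differs and the contrast shifts. Under no treatment effect, the on-treatment and treatment-policy targets are both zero, so no choice of estimand can justify that shift. With a true effect, whether LOCF is biased at all depends on the estimand, which is not stated. No second analysis is planned that would show how far the result depends on the rule.

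**Working it through.** **Inputs from Section VI.** Difference 4 points, SD of change 4.86, two-sided alpha 0.05, 72 randomised (36 per arm), 60 completing (30 per arm), so 12 lost.

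**Assumed, because the documents give none of it.** Split of losses by arm; mean changes of -8 (suvorexant) and -4 (placebo), or -6 in both under no effect; losses unrelated to outcome within arm; no remote ISI unless stated; and *c*, the average fraction of the Week-4 change that is carried forward. *c* is the share of lost women with a V3 score times the fraction of the Week-4 change which that score shows. I use *c* = 0 (all carry baseline), 0.2 (half have a V3 score worth 40%) and 0.5 (all have one worth 50%).

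**1. The plan's own figure.** Noncentrality 4 / (4.86 × √(2/30)) = 3.19, which gives 88.0% power at 30 per arm (t-test). About 25 per arm would give 80%. The stated 80% is therefore conservative, and this headroom absorbs some loss.

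**2. LOCF estimate.** With *d* losses among 36, an arm's mean change is T × [1 - (d/36)(1 - c)].
- 6/6 (suvorexant/placebo), c = 0: 8 × 30/36 - 4 × 30/36 = 3.33
- 9/3, c = 0: 8 × 27/36 - 4 × 33/36 = 6.00 - 3.67 = 2.33
- 9/3, c = 0.5: 8 × (1 - 4.5/36) - 4 × (1 - 1.5/36) = 7.00 - 3.83 = 3.17
- 3/9, c = 0: 8 × 33/36 - 4 × 27/36 = 7.33 - 3.00 = 4.33

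The on-treatment target is 4. If women who leave suvorexant end at the placebo mean, the treatment-policy target is 4 × (36 - d)/36, where d is the number lost on suvorexant: 3.33, 3.00 and 3.67 for 6/6, 9/3 and 3/9.

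**3. No true effect, both arms -6.** The bias is 6 × (1 - c) × (difference in losses)/36. At 9/3 this is 6 × 6/36 = 1.0 point against suvorexant when c = 0, and 0.5 when c = 0.5. At 3/9 it has the same size in favour of suvorexant. At 6/6 it is zero.

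**4. Power and rejection, by simulation.** Analysis of covariance on baseline, assuming baseline SD 3, Week-1 change SD 3.5 and correlation 0.6 with the Week-4 change; an unadjusted t-test was run as a check. The ranges cover c = 0 to 0.5 and both analyses.

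| Losses (suvorexant/placebo) | LOCF estimate, true 4 | Treatment-policy target | Power | Bias, no effect | Rejection, no effect |
|---|---|---|---|---|---|
| 6/6 | 3.33–3.67 | 3.33 | 82–89% | 0 | 3–4% |
| 9/3 | 2.33–3.17 | 3.00 | 46–80% | 0.5–1.0 against suvorexant | 6–11% |
| 3/9 | 4.17–4.33 | 3.67 | 94–97% | 0.5–1.0 for suvorexant | 6–11% |

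At 3/9 nearly all false rejections favour suvorexant, where the nominal rate in that direction is 2.5%. At 8/4 or 4/8, rejection is about 5–6%.

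**5. How likely is such a split?** If loss is unrelated to arm, 12 losses drawn from 36 + 36 women split 9/3 or more unevenly, in either direction, with probability 0.11 (hypergeometric).

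**6. Effect of remote collection.** If 8 of the 12 give a Week-4 remote ISI (c = 0 or 0.2 for the rest), LOCF gives 2.77–2.90 at 9/3 (treatment-policy target 3.00) and 3.84–3.90 at 3/9 (target 3.67). Rejection under no effect is 4.3–5.2%.

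**The case against.** The strongest defence is that the plan already limits the problem. It collects questionnaires remotely from women who stop or are dropped, and step 6 shows that good remote response nearly removes the harm. Balanced losses cost little, and a 9/3 split is uncommon by chance. Three of the four treatment weeks follow V3, so many lost women would have a V3 score; at that milder end, LOCF at 9/3 lies close to the treatment-policy target (3.17 against 3.00). All of this stands, and it sets the size of the point.

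Nor is a repeated-measures model better under every estimand. Without off-treatment data it estimates the on-treatment effect: 4.0 at 9/3 under missing at random, which is 1.0 above the treatment-policy target. The replacement must therefore be tied to the estimand.

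The defence that LOCF is simply conservative does not stand, because at 3/9 it favours suvorexant.

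A reader might also infer more than the documents support:
- That this trial's type I error is inflated, or that LOCF favours suvorexant here. No section gives losses by arm, so neither can be said.
- That the trial is underpowered. With balanced losses, power stays above the stated 80%.
- That an early remote ISI would be used as the Week-4 value. In Section IV the remaining questionnaires most naturally mean those still scheduled, and the remote route in Section V belongs to the final visit. Only the Off-Study Criteria leave the date open.

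**Conclusion.** The point holds as a cheap improvement. The textual gap is certain: one single-imputation rule, no estimand, no missing-data sensitivity analysis, and no date for the final questionnaires of women dropped early.

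The consequence is conditional. It needs clearly unequal losses together with few remote ISIs. In that case LOCF can create a difference of about 0.5–1.0 points where none exists, in either direction, and can lower or raise the estimate when there is an effect. The figures rest on the assumed arm changes, splits and Week-1 response. They show what the rule can do, not what will happen in this trial.

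**What to change.** 1. State the estimand. Date the already planned remote ISI of women dropped early (Off-Study Criteria) at the scheduled Week-4 date, and say whether an ISI obtained after an off-study event, such as starting a sleep medication, counts in the primary analysis.
2. Replace LOCF as the primary approach with a likelihood-based repeated-measures model of the V3 and V4 ISI in all randomised women: treatment by visit, baseline ISI by visit, unstructured covariance, Week-4 contrast. State that it assumes missing at random and that, without off-treatment data, it targets the on-treatment effect. If a treatment-policy estimand is chosen and remote ISIs are few, use reference-based multiple imputation instead.
3. Add one reference-based or delta-adjusted multiple-imputation sensitivity analysis, and keep LOCF at most as a further sensitivity analysis.

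The cost is SAP wording, one fixed date and slightly more analysis work. No visit or participant is added, because the V3 ISI and the remote questionnaires are already planned. The downside is reliance on missing at random, which the sensitivity analysis is there to test. The changes should be settled before unblinding.

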Summary of preliminary data: Taken together these preliminary data highlight that for women with hot flash-related insomnia syndromes who would be eligible for our proposed trial: 1) the extent of their sleep disturbance is high, 2) sleep maintenance problems dominate the time spent awake, and 3) WASO time persists into the final third of the night. In addition, within-person night-to-night variability of SOL and WASO is low on both subjective and actigraphic measures. In addition, psychological indicators of hyperarousal correlate with the degree of sleep disruption among women with hot flashes. *In summary, women with a hot flash-related insomnia syndrome have substantial sleep continuity problems that are composed of a distinctive profile of sleep disruption dominated by reduced TST and large amounts of WASO, which persists throughout the night. These characteristics of hot flash-related insomnia make this population an ideal one in whom to investigate the efficacy of suvorexant.*

II. SPECIFIC AIMS

PRIMARY AIM: To determine the effect of suvorexant on insomnia symptoms in peri- and postmenopausal women with a chronic insomnia syndrome related to nighttime hot flashes using a randomized placebo-controlled trial.

HYPOTHESIS: Women randomized to suvorexant will show greater improvement in insomnia symptoms compared with women randomized to placebo.

SECONDARY EXPLORATORY HYPOTHESES

1. Relative to those assigned to placebo, women randomized to suvorexant will show:
 - a. Greater reduction in wake-time after sleep-onset.
 - b. Greater improvement in mood, anxiety, and quality of life.
 - c. Greater reduction in hot flash frequency.
2. Improvement in insomnia symptoms will be positively correlated with improvement in mood, anxiety, hot flashes, and quality of life.

III. SUBJECT SELECTION

Inclusion/Exclusion Criteria

We plan to enroll up to 90 women who meet the following criteria in order to have 72 women randomized in a 1-to-1 ratio to suvorexant 10-20 mg or equivalent placebo in order to have 60 women (30 per arm) complete the trial.

Inclusion criteria:

1. Age 40–65 years
2. Peri- or postmenopausal women, with menopause status determined by menstrual marker. Women who underwent bilateral oophorectomy will be enrolled if 6+ months from surgery. Those who underwent hysterectomy with ovarian preservation, or who have amenorrhea from progesterone-secreting IUD, or endometrial ablation may be enrolled based on clinical assessment and judgment.

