Suvorexant can cause next-day mental impairment, and this risk is increased with higher doses if instructions are not carefully followed. Subjects in their second, third, or fourth week of study drug dosing should avoid driving and other activities requiring full mental alertness in the morning. Subjects in their first week of study drug dosing should also be careful about driving in the morning, because there is individual variation in people's sensitivity to suvorexant. Before taking the study drug subjects will be advised to read the FDA-approved Medication Guide.

The participant will be informed that the study medication suvorexant must only be taken by the subject alone, the person for whom it was intended. In addition, the study medication must be kept out of the reach of children or persons with limited ability to read and understand.

Reproductive Risks

There are no adequate and well-controlled studies of either suvorexant in pregnant women. The study drug should be used during pregnancy only if the potential benefit justifies the potential risk to the fetus. The effect of the study drug on infants or unborn children is not known, and, as with any new drug, there is the potential for very serious harmful effects. In order to prevent any possible damage to an unborn child, subjects must not become pregnant while participating in this research study and for 30 days after finishing the study. Contraceptive methods must be used during and immediately after this study by women who are sexually active and have reproductive potential. Women using hormones will be excluded from study participation. Study participants will be required to use barrier methods of contraception if they are of reproductive potential. The following is a list of acceptable birth control methods: female sterilization, intrauterine device (IUD), diaphragm with spermicide, male condom, female condom, cervical cap, etc.

Women who are pregnant or breastfeeding will be excluded from the study. A pregnancy test will be conducted at screening for all subjects. If a subject thinks she might be pregnant at any time during this study, she will be advised to contact the study physician or research assistant immediately. In addition, participants will be informed that they cannot use hormonal contraception as a primary form of birth control until after medication discontinuation. At each visit these precautions will be discussed thoroughly with the subject.

Psychological Risks

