Answering questions on the research instruments and questionnaires used to evaluate psychological symptoms can be upsetting to some subjects.

Blood Sampling

The risks associated with phlebotomy are minimal and include hematoma, pain, infection, and fainting spells. The amount of blood drawn for this study is approximately 15 mL (3 teaspoons) and is not enough to cause harm to the subjects. All blood draws will be performed by trained personnel who use standard sterile techniques.

Objective hot flash monitor

There are no significant risks associated with skin-conductance methodologies. The Biolog ambulatory recorder is an 8-ounce, 9V battery-powered device measuring 1.3 x 2.8 x 5 inches that is worn in a pouch and suspended by a shoulder strap, similar to a Holter monitor. It is a portable and ambulatory device. There is a minor risk of skin irritation and reddening from the adhesive gel required to attach the electrodes to the sternum. This irritation is typically mild and resolves within a few days.

Actigraphy watch

There are no significant risks associated with the actigraphy watch. The actigraphic watch is a light-weight sports watch that can be worn continuously and can get wet.

Procedures to Minimize Risks

All study procedures will be approved by the Partners (renamed Mass General Brigham) IRB before being initiated. To avoid serious adverse effects from medications, the following precautions will be taken:

A urine HCG test will be performed on all subjects at the screening visit to confirm that subjects are not pregnant. This procedure for confirming the absence of pregnancy will be followed regardless of whether or not the subject informs us that she is sexually active and regardless of the specific type of contraception that is being used. All subjects who are of reproductive potential will be advised to use a barrier method of contraception for the duration of the study and after study completion until menses resume. Adverse events will be monitored at each study visit.

The dose of study medication will be reduced to 10-mg/day if a participant is unable to tolerate the target dose of 20-mg/day.

Participants with conditions which are contraindications to suvorexant use will be excluded.

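### The only scheduled pregnancy test is at the screening visit, nominally 7 days before study drug is first dispensed, and it is not repeated before randomization

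*Combined protocol and SAP*

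**What the plan says.** Section VII describes the pregnancy test twice. Procedures to Minimize Risks says "A urine HCG test will be performed on all subjects at the screening visit to confirm that subjects are not pregnant", and Reproductive Risks says "A pregnancy test will be conducted at screening for all subjects". The first of these adds that the test applies whatever the woman reports about sexual activity and whatever contraception she uses. In the Table of Procedures (Section V), the screening-assay row that contains HCG has one mark, at V1.

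Study drug is first handed out at V2, the Randomization Visit (IV, Treatment Assignment and Randomization). The table puts V1 at study week 0 and V2 at week 1, and the text on drugs to be used gives a run-in of one week. At V2, final eligibility is settled from the diary and the laboratory results already in hand. No new test is named.

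The Pre-Screening section allows for slippage: "The ISI may be administered again over the phone before Visit 1 or Visit 2, if one of these visits has been delayed". It makes no such provision for HCG, and no upper limit on the V1–V2 interval is stated.

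On who could be pregnant, the inclusion criteria admit women from age 40: "Peri- or postmenopausal women, with menopause status determined by menstrual marker". Reproductive Risks accepts that some will have reproductive potential. It says fetal effects are not known and that "as with any new drug, there is the potential for very serious harmful effects". After screening the plan relies on contraception, discussion of precautions at each visit, and self-report: "If a subject thinks she might be pregnant at any time during this study, she will be advised to contact the study physician". Pregnancy is both an exclusion and an off-study criterion.

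**The concern.** V2 is the last point at which a pregnancy can be found before any exposure and randomization withheld. The negative result relied on at that visit is nominally a week old, and older if V2 slips. A woman whose pregnancy was too early to show at V1, but would show at V2, would be randomized and dosed unless someone suspects it.

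The remaining safeguards do not fully close this gap. Contraception reduces new conceptions but does not detect an existing one. The study's counselling starts at V1, so it cannot prevent a conception shortly before V1. Self-suspicion may also be a weak signal here. Cycles may be irregular in perimenopause, and the inclusion criteria allow, on clinical judgment, women without periods because of a progesterone-secreting IUD or an endometrial ablation. The protocol itself does not let contraception or self-report stand in for a test at screening, yet it relies on them from V1 to first dose.

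What is at stake is participant and fetal safety. The primary endpoint, the analysis and the sample size are not affected.

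**Working it through.** **Scheduled tests.** From the Table of Procedures and the two statements in Section VII: V1 = 1; V2, V3 and V4 = 0. The prose and the table agree, so this does not depend on how the table was read.

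**Age of the HCG result at first dispensing.** Days = 7 × (week of V2 − week of latest test).
- As planned: 7 × (1 − 0) = 7 days. This reproduces the one-week run-in in the text.
- If V2 is delayed by d days: 7 + d. The documents give no value or ceiling for d, so no delay scenario is carried further.
- With a test at V2: 0 days, whatever the delay.

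**Expected number of pregnancies in the gap.** Expected = 72 × share with reproductive potential × annual pregnancy rate × 7/365.
- 72 is the planned number randomized (Section III, and Power and sample size).
- The share and the rate are not in the documents. Assumed ranges: share 10% to 50%, rate 1% to 10% per year.
- Low end: 72 × 0.10 × 0.01 × 7/365 = 0.0014.
- High end: 72 × 0.50 × 0.10 × 7/365 = 0.069.
- On suvorexant, with 1:1 allocation, half of each: 0.0007 to 0.035.

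If the pregnancy rate is constant over time, as many pregnancies cross the detection threshold in a 7-day window as are conceived in one. The figure can therefore be read as pregnancies that become detectable between V1 and V2, which is what a V2 test would find. It is not a count of every conception present at V2.

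**Number of extra tests.** At most 72 if only women otherwise ready for randomization are tested, and fewer when limited to women of reproductive potential.

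**The case against.** The strongest reply is that the event is very rare. On the assumed ranges, an exposed pregnancy on suvorexant would arise in the gap about once in 29 trials of this size (1/0.0345) at the high end and once in about 1,450 (1/0.00069) at the low end. The high end pairs 50% reproductive potential with 10% per year despite contraception. Participants must average at least two hot flashes a day. Some will have had oophorectomy or hysterectomy. FSH, estradiol and progesterone are measured at V1 and inform reproductive status. Staff discuss precautions at every visit, including the day of dispensing, and nothing bars an unscheduled test. The plan also breaks no rule of its own: it says it tests at screening, and it does. All of this stands, and it sets the severity low. None of it supplies a current test result at V2.

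A reader might infer more than the documents support:
- **That a V2 test covers every conception between V1 and V2.** It does not. As general physiology rather than anything in the documents, urine HCG is not positive within days of conception. The test would mainly find conceptions from before V1 that were too early to show then. The share of study days before V2 is therefore not a measure of coverage.
- **That long delays to V2 are expected.** The Pre-Screening sentence concerns repeating the ISI and gives no length or frequency. V2 is tied to the return of one-week diaries and devices in a study of about six weeks. Only the absence of a ceiling is established.
- **That the barrier-contraception wording should be made uniform as part of this fix.** Reproductive Risks says "Study participants will be required to use barrier methods of contraception if they are of reproductive potential", while Procedures to Minimize Risks says "All subjects who are of reproductive potential will be advised to use a barrier method of contraception". The difference is real, but the list of acceptable methods under Reproductive Risks includes sterilization and IUD, which are not barrier methods. Copying the stricter sentence would spread that conflict. The same section already obliges sexually active women with reproductive potential to use contraception.

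**Conclusion.** The point holds as a low-severity, cheap improvement. One pregnancy test is scheduled, at V1. First dispensing is nominally 7 days later, with no stated maximum interval, and a pregnancy that becomes detectable in between is found before dosing only if it is suspected and reported.

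The likely yield is about 0.001 to 0.07 pregnancies across both arms for a 7-day gap, and that range rests wholly on the assumed share and rate. The recommendation therefore depends on the possible seriousness of fetal exposure, which the protocol itself acknowledges, and on how little the test costs. The documents do not support calling the trial unsafe or the screening procedure defective.

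**What to change.** Repeat the urine HCG at V2, before randomization and dispensing, for women of reproductive potential. Mark it in the V2 column of the Table of Procedures, add a matching sentence under Procedures to Minimize Risks, and state that a woman with a positive result is not randomized.

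The cost is at most about 72 extra dipsticks at an existing office visit, plus a few lines of amendment. Because the result is available on the day, a delayed V2 needs no separate rule. Blinding, endpoint and sample size do not change. The limit should be stated openly: very recent conceptions, and those during the 28 days on drug, are not detected and still depend on contraception, counselling and self-report.
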